### 2.2. Study Objective(s) and Endpoint(s)

Objectives	Endpoints
Primary Objectives	Primary Endpoints

 
To investigate the safety and tolerability of GSK3640254 following single and repeated daily administration
 
	
 
GSK3640254 safety parameters: adverse events; post-baseline values and changes over time of clinical laboratory evaluations (haematology, clinical chemistry, urinalysis), vital signs, and ECG parameters from predose values
 

Secondary Objectives	Secondary Endpoints

 
To describe the PK of GSK3640254 following single and repeated daily administration
 
	
 
GSK3640254 PK parameters:  Part 1 (single dose): AUC(0-24), AUC(0-tlast), AUC(0-inf), Cmax, C24, tmax, tlag, t1/2, Clast, tlast, CL/F.  Part 2 (Repeated QD doses for 14 days): Day 1: AUC(0-24), Cmax, C24, tmax, tlag Day 14: AUC(0-<math>\tau</math>), Cmax, C<math>\tau</math>, tmax, t1/2, and CL/F
 

 
To examine dose proportionality following single and repeated doses of GSK3640254
 
	
 
GSK3640254 Single dose: AUC(0-inf), Cmax.
 
Repeat dose AUC(0-<math>\tau</math>), Cmax, C<math>\tau</math>
 

 
To assess accumulation of GSK3640254
 
	
 
Accumulation ratios: R AUC(0-<math>\tau</math>), R(Cmax), R (C<math>\tau</math>)
 

 
To assess time to steady-state of GSK3640254
 
	
 
Pre-dose concentrations on Day 2 -14 (Part 2)
 

Exploratory Objectives	Exploratory Endpoints

 
To assess the exposure response relationship between GSK3640254 and safety parameter, including QTcF following single and repeated administration
 
	
 
Change-from-baseline QTcF (<math>\Delta</math>QTcF)
 

 
To investigate the biotransformation of GSK3640254 in plasma and urine
 
	
 
Provide samples of plasma and urine for the identification of any compound derived metabolite(s)
 


 
As available, to assess the impact of food on the PK of GSK3640254
 
	
 
GSK3640254 single dose Cmax, AUC(0-inf), and C24
 

Note: The exploratory endpoints may be analyzed once GSK3640254 clinical development continues.

## 2.3. Study Design

Overview of Study Design and Key Features	

The diagram illustrates the study design. Part 1 (SAD) consists of two cohorts, Cohort 1 and Cohort 2, each with four periods of treatment. Cohort 1 doses are 1 mg, 10 mg, 100 mg, and 400 mg. Cohort 2 doses are 3 mg, 30 mg, 200 mg, and 700 mg. Part 2 (MAD) consists of five cohorts: Cohort 3 (50 mg QD), Cohort 4 (100 mg QD), Cohort 5 (200 mg QD), Cohort 6 (320 mg QD), and an Expansion Cohort (200 mg QD). All cohorts in Part 2 have 14 days of treatment and n=8 participants (A/P=6/2), except for the Expansion Cohort which has n=24 (A/P=18/6).
	
Design Features	
 
Two part, Phase 1, double-blind (sponsor-unblinded), randomized, placebo controlled, single- and repeat-dose escalation study.
 
 
Part 1 (SAD):
 
 
SAD portion will be conducted in an interlocking fashion with 2 separate cohorts of 8 healthy participants each. Each of these 2 cohorts will contain up to 4 escalating doses of GSK3640254.
 
In each escalating period and Cohort, 6 participants will be randomized to GSK3640254 and 2 participants will be randomized to placebo.
 
Participants in Cohort 1 and Cohort 2 will follow the same randomization strategy with alternating ascending doses with 4-period crossover, placebo-controlled.
 
 
Part 2 (MAD):
 
 
Part 2 consists of 4 ascending repeat-dose cohorts (Cohorts 3 to 6), each with 8 participants (active/PBO=6/2) who will receive a once-daily dose of GSK3640254 or PBO for 14 days.
 
Part 2 also includes an Expansion Cohort which will be conducted at the conclusion of cohort 5.
 
The Expansion Cohort will evaluate the rate of GI intolerability in 24 participants (active/PBO =18/6).
 

Dosing	
Part 1 (SAD):
 
 
The dose for Part 1 Cohort 1 of this study were 1 mg for Period 1, 10 mg for Period 2, 100 mg for Period 3 and 400 mg for Period 4.
 
The dose for Part 1 Cohort 2 of this study will be 3 mg for Period 1, 30 mg for Period 2, 200 mg for Period 3 and 700 mg for Period 4.
 
 
Part 2 (MAD):
 
 
The dose for Part 2 of this study were 50 mg for Cohort 3, 100 mg for Cohort 4, 200 mg for Cohort 5 and the expansion cohort, and 320 mg for cohort 6.
 

Overview of Study Design and Key Features																																																			
	All doses were administered in fed condition.																																																		
Time & Events	
 
Refer to Appendix 2: Schedule of Activities
 
																																																		
Treatment Assignment	
Part 1 (SAD):
 
 
Participants in either Cohort 1 or Cohort 2 will be assigned to 1 of the 4 treatment sequences in a cross-over, and each participant will receive placebo once.
 
 
  
 Cohort 1	Period 1	Period 2	Period 3	Period 4	
   
 Sequence 1	Placebo	Dose 3	Dose 5	Dose 7	
 
 Sequence 2	Dose 1	Placebo	Dose 5	Dose 7	
 
 Sequence 3	Dose 1	Dose 3	Placebo	Dose 7	
 
 Sequence 4	Dose 1	Dose 3	Dose 5	Placebo	
  
 
  
 Cohort 2	Period 1	Period 2	Period 3	Period 4	
   
 Sequence 1	Placebo	Dose 4	Dose 6	Dose 8	
 
 Sequence 2	Dose 2	Placebo	Dose 6	Dose 8	
 
 Sequence 3	Dose 2	Dose 4	Placebo	Dose 8	
 
 Sequence 4	Dose 2	Dose 4	Dose 6	Placebo	
  
 
Part 2 (MAD):
 
 
In Cohorts 3 to 6, 8 participants per cohort (active/PBO=6/2) will receive a once-daily dose of GSK3640254 or PBO for 14 days.
 
In the Expansion Cohort, 24 participants (active/PBO=18/6) will receive a once-daily dose (200 mg) of GSK3640254 or PBO for 14 days
 
	Cohort 1	Period 1	Period 2	Period 3	Period 4	Sequence 1	Placebo	Dose 3	Dose 5	Dose 7	Sequence 2	Dose 1	Placebo	Dose 5	Dose 7	Sequence 3	Dose 1	Dose 3	Placebo	Dose 7	Sequence 4	Dose 1	Dose 3	Dose 5	Placebo	Cohort 2	Period 1	Period 2	Period 3	Period 4	Sequence 1	Placebo	Dose 4	Dose 6	Dose 8	Sequence 2	Dose 2	Placebo	Dose 6	Dose 8	Sequence 3	Dose 2	Dose 4	Placebo	Dose 8	Sequence 4	Dose 2	Dose 4	Dose 6	Placebo
Cohort 1	Period 1	Period 2	Period 3	Period 4																																															
Sequence 1	Placebo	Dose 3	Dose 5	Dose 7																																															
Sequence 2	Dose 1	Placebo	Dose 5	Dose 7																																															
Sequence 3	Dose 1	Dose 3	Placebo	Dose 7																																															
Sequence 4	Dose 1	Dose 3	Dose 5	Placebo																																															
Cohort 2	Period 1	Period 2	Period 3	Period 4																																															
Sequence 1	Placebo	Dose 4	Dose 6	Dose 8																																															
Sequence 2	Dose 2	Placebo	Dose 6	Dose 8																																															
Sequence 3	Dose 2	Dose 4	Placebo	Dose 8																																															
Sequence 4	Dose 2	Dose 4	Dose 6	Placebo																																															
Interim Analysis	
 
All preliminary safety, tolerability, and available PK data were reviewed internally at VH/GSK prior to each dose escalation. Safety data (labs, vital signs, ECG, AEs, SAEs) were reviewed by the PI/Sub-I and VH/GSK study team after completion of each dose level.
 
																																																		

## 2.4. Statistical Hypotheses

The main purpose of this study is to assess the safety, tolerability and PK of single and repeated oral doses of GSK3640254 in healthy volunteers. No formal hypotheses are to be tested and no statistical testing will be performed.

### 3. PLANNED ANALYSES

#### 3.1. Interim Analyses

All preliminary safety, tolerability, and available PK data were reviewed internally at VH/GSK prior to each dose escalation. Safety data (labs, vital signs, ECG, AEs, SAEs) will be reviewed by the PI/Sub-I and VH/GSK study team after completion of each dose level.

At each dose, the Bayesian probability of an individual exceeding the Cmax stopping criteria in Part 1 and the Bayesian probability of an individual exceeding the AUC stopping criteria in Part 2 will be calculated and compared with 50%. This will be used to help selection of the next dose together with safety and tolerability data. The Bayesian probability will be based on Whitehead's model shown below [Whitehead, 2001] using non-informative prior for model parameters.

$$y_{ij} = \theta_1 + \theta_2 d_{ij} + s_i + \epsilon_{ij} \quad [1]$$

Where  $y_{ij}$  is log-PK of  $i$ -th participant to  $j$ -th dose,  $d_{ij}$  is  $j$ -th log-dose administered to  $i$ -th participant.  $\theta_1$  and  $\theta_2$  are population intercept and slope, respectively.  $s_i$  is random effect of  $i$ -th participant and  $\epsilon_{ij}$  is random error of  $i$ -th participant in  $j$ -th dose. Note that, from the first to the second dose in Part 1 of the study, we will assume that the PK is dose-proportional for the model.

When intra-participant PK variability cannot be estimated early in Part 1 (i.e., early on in the study when there is not sufficient information to estimate intra-participant variability) and for conducting prediction of all doses in Part 2, the same Whitehead's model will be used for Bayesian probability calculations as below.

$$y_i = \theta_1 + \theta_2 d_i + \epsilon_i \quad [2]$$

Where  $y_i$  is log-PK of  $i$ -th participant,  $d_i$  is the log-dose administered to  $i$ -th participant.  $\theta_1$  and  $\theta_2$  are population intercept and slope, respectively and  $\epsilon_i$  is random error of  $i$ -th participant. Note that, from the first to the second dose in Part 2 of the study, we will assume that the PK is dose-proportional for the model.

#### 3.2. Final Analyses

The final planned primary analyses will be performed after the completion of the following sequential steps:

1. All participants have completed the study as defined in the protocol
2. All required database cleaning activities have been completed and final database release (DBR) and database freeze (DBF) has been declared by Data Management.
3. All criteria for unblinding the randomization codes have been met.
4. Randomization codes have been distributed according to RandAll NG procedures.

Data will be listed and summarized according to GlaxoSmithKline reporting standards, where applicable. Listings will be sorted by subject, day and time, noting treatment; summaries will be presented by treatment, day, and time. Unless stated otherwise, descriptive summaries will include n, mean, standard deviation (SD), coefficient of variation (%CV), median, minimum, and maximum for continuous variables, whereas n and percent will be used as summary statistics for categorical variables, and geometric mean, 95% confidence interval (CI), and the between-participant CV (%CVb) for the log-transformed PK parameters. Baseline or predose assessment is the last available assessment prior to time of the first dose unless it is specified otherwise. If there are multiple assessments collected on the same scheduled time, the average of these assessments will be used. For tabulated safety summaries, only the scheduled assessments will be included in the summary tables. Version 9.3 or higher of the SAS system will be used to analyse the data as well as to generate tables, figures, and listings.

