**5.2. Baseline Definitions**

For all endpoints (except as noted in baseline definitions) the baseline value will be the latest pre-dose assessment with a non-missing value, including those from unscheduled visits. If time is not collected, Day 1 assessments are assumed to be taken prior to first dose and used as baseline.

Parameter	Study Assessments Considered as Baseline				Baseline Used in Data Display
	Screening	Day -2	Day -1	Day 1 (Pre-Dose)	
Lab	X	X			Day -2 in each period
ECG	X	X	X	X	Day 1(Pre-Dose) in each period

Parameter	Study Assessments Considered as Baseline				Baseline Used in Data Display
	Screening	Day -2	Day -1	Day 1 (Pre-Dose)	
Vital Signs	X		X		Day -1 in each period

Unless otherwise stated, if baseline data is missing no derivation will be performed and baseline will be set to missing.

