### Protocol Required Safety Laboratory Assessments

Laboratory Assessments	Parameters			
Hematology	Platelet Count	RBC Indices: MCV MCH %Reticulocytes		WBC count with Differential : Neutrophils Lymphocytes Monocytes Eosinophils Basophils
	RBC Count			
	Hemoglobin			
	Hematocrit			
Clinical Chemistry	BUN	Potassium	Aspartate Aminotransferase (AST)/ Serum Glutamic-Oxaloacetic Transaminase (SGOT)	Total bilirubin
	Creatinine	Sodium, Chloride, Bicarb	Alanine Aminotransferase (ALT)/ Serum Glutamic-Pyruvic Transaminase (SGPT)	Total Protein
	Glucose (non-fasting)	Calcium, Magnesium, Phosphate	Alkaline phosphatase	Fasting Lipid Panel (Cholesterol, Triglycerides, HDL, LDL)
Routine Urinalysis	
 
• Specific gravity
 
• pH, glucose, protein, blood, ketones, bilirubin, urobilinogen, nitrite, leukocyte esterase by dipstick
 
• Microscopic examination (if blood or protein is abnormal)
 
			

The following summaries will be provided:

- Laboratory values for hematology, clinical chemistry, and urinalysis by visit and by treatment
- Laboratory values change from baseline for hematology and clinical chemistry by visit and by treatment group
- The number and percentage of subjects with on-treatment laboratory abnormalities worsened from baseline by maximum grade for haematology, clinical chemistry and urinalysis.
- Treatment emergent laboratory toxicities

The following listings will be provided:

- Laboratory values for haematology, clinical chemistry, and urinalysis
- Laboratory values of potential clinical importance for hematology, clinical chemistry and urinalysis (potential clinical importance criteria are specified in Section 12.8.1)
- Laboratory results identified as adverse events
- Subjects with grades 2 or higher laboratory toxicities

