#### **7.2.3.3. Hepatobiliary (Liver)**

Liver monitoring/stopping event reporting will be summarized by treatment group. A summary of hepatobiliary laboratory abnormalities will be produced.

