### 11.5.2. Reporting Standards

General

 
The current GSK Integrated Data Standards Library (IDSL) will be applied for reporting, unless otherwise stated (IDSL Standards Location: https://spope.gsk.com/sites/IDSLLibrary/SitePages/Home.aspx): 
 
4.03 to 4.23: General Principles
 
5.01 to 5.08: Principles Related to Data Listings
 
6.01 to 6.11: Principles Related to Summary Tables
 
7.01 to 7.13: Principles Related to Graphics
 
 
 
Do not include subject level listings in the main body of the GSK Clinical Study Report. All subject level listings should be located in the modular appendices as ICH or non-ICH listings
 
Statistical analyses of the pharmacokinetic parameter data will be the responsibility of Clinical Statistics, GSK.
 

Formats

 
GSK IDSL Statistical Principles (5.03 & 6.06.3) for decimal places (DP's) will be adopted for reporting of data based on the raw data collected, unless otherwise stated.
 
Numeric data will be reported at the precision collected on the eCRF.
 
The reported precision from non eCRF sources will follow the IDSL statistical principles but may be adjusted to a clinically interpretable number of DP's.
 

Planned and Actual Time

 
Reporting for tables, figures and formal statistical analyses: 
 
Planned time relative to dosing will be used in figures, summaries, statistical analyses and calculation of any derived parameters, unless otherwise stated.
 
The impact of any major deviation from the planned assessment times and/or scheduled visit days on the analyses and interpretation of the results will be assessed as appropriate.
 
 
 
Reporting for Data Listings: 
 
Planned and actual time relative to study drug dosing will be shown in listings (Refer to IDSL Statistical Principle 5.05.1).
 
Unscheduled or unplanned readings will be presented within the subject's listings.
 
 
 

Unscheduled Visits

 
• Unscheduled visits will not be included in summary tables and/or figures.
 
• All unscheduled visits will be included in listings.
 
	

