## 11.6. Appendix 6: Derived and Transformed Data

### 11.6.1. General

Multiple Measurements at One Analysis Time Point

 
Mean of the measurements will be calculated and used in any derivation of summary statistics but if listed, all data will be presented.
 
Participants having both High and Low values for Normal Ranges at any post-baseline visit for safety parameters will be counted in both the High and Low categories of “Any visit post-baseline” row of related summary tables. This will also be applicable to relevant Potential Clinical Importance summary tables.
 

Study Day

 
Calculated as the number of days from First Dose Date:           
 
Ref Date = Missing → Study Day = Missing
 
Ref Date < First Dose Date → Study Day = Ref Date – First Dose Date
 
Ref Date ≥ First Dose Date → Study Day = Ref Date – (First Dose Date) + 1
 
 
 

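### The SAP's scheduled-only rule has no exception for the worst-case, toxicity and hepatobiliary lab tables, so a peak seen only on an unscheduled repeat can be missing from them while the listings show it

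*SAP*

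**What the plan says.** SAP 3.2 (Final Analyses) sets two general rules. The first is "For tabulated safety summaries, only the scheduled assessments will be included in the summary tables". The second is "If there are multiple assessments collected on the same scheduled time, the average of these assessments will be used".

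The appendices repeat both. SAP 11.5.2 says "Unscheduled visits will not be included in summary tables and/or figures", followed by "All unscheduled visits will be included in listings". SAP 11.6.1 says of several measurements at one time point: "Mean of the measurements will be calculated and used in any derivation of summary statistics but if listed, all data will be presented". SAP 11.7.1 points the same way for withdrawn participants: all their data are listed, but only the planned data go into tables.

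Against this, SAP 7.2.2 promises "The number and percentage of subjects with on-treatment laboratory abnormalities worsened from baseline by maximum grade" for haematology, chemistry and urinalysis, together with summaries of treatment-emergent toxicities. SAP 7.2.3.3 adds: "A summary of hepatobiliary laboratory abnormalities will be produced". The display list in SAP 11.12.5 turns these into:

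- worst-case tables 3.11, 3.15 and 3.19 (Part 1) and 3.38, 3.42 and 3.46 (Part 2);
- toxicity tables 3.12 and 3.16, and 3.39 and 3.43;
- hepatobiliary tables 3.21 and 3.48.

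No programming note for any of them mentions unscheduled or repeated results.

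**The concern.** A scheduled-only rule suits a table of means by visit, where every participant should contribute once per nominal time. It does not suit a table whose purpose is each participant's worst value. Laboratory evaluations are part of the primary safety endpoint, and the protocol triggers extra samples when something looks abnormal. The rule therefore removes values from the participants in whom the maximum is of most interest.

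Tables presented as worst case could then show a lower grade than the same report's Grade 2 or higher listings (35 and 36 for Part 1, 76 and 77 for Part 2). A reader who relies on the tables would see a milder profile than was recorded.

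**Working it through.** There is no figure in the plan to reproduce, so the check is a reading of the texts plus simple arithmetic.

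**1. Do off-schedule lab values arise?** Yes, from three places in the protocol.
- Section 9 allows unscheduled samples for safety or technical reasons.
- Section 9.4.4 requires clinically significant abnormal values to be repeated until they settle.
- Appendix 7 sets weekly liver monitoring after ALT of at least 3xULN, and twice-weekly monitoring when bilirubin or INR is also raised.

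**2. Does any text let them into the worst-case tables?** No.
- SAP 3.2 and 11.5.2 are unqualified.
- SAP 11.6.1 mentions a row for any post-baseline visit, but only to say that a participant can count as both high and low.
- The house display standards apply only where the plan does not state otherwise, and here it does.

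**3. Direction of the effect.** Let S be a participant's scheduled post-baseline grades and U the unscheduled ones. Since max(S) ≤ max(S and U together), the tabulated maximum can equal the true maximum or fall below it, never above. With assumed values: scheduled Day 8 is Grade 1, an unscheduled Day 9 repeat is Grade 3, and scheduled Day 10 is Grade 2. The table shows Grade 2 and the listing shows Grade 3.

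**4. Ceiling per participant.** Group sizes come from Protocol 5.1 and the pooling in SAP 5.1.
- Six on active drug: 1/6 = 16.7 points.
- 200 mg once daily, Cohort 5 plus expansion, 6 + 18 = 24: 1/24 = 4.2 points.
- Pooled MAD placebo, 4 x 2 + 6 = 14: 1/14 = 7.1 points.
- Pooled SAD placebo, 2 cohorts x 4 periods x 2 = 16: 1/16 = 6.3 points.

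These are the most that one participant can move one category. They are not estimates.

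**5. Same-time averaging (secondary).** The clearest case is Protocol Appendix 2. When a local sample is needed, a central sample is taken at the same time, and a local result used for a decision is entered in the CRF. Two results can then share one scheduled time. For results a and b in multiples of ULN, the mean is below 3 when a + b < 6. With assumed ALT values:

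| a | b | mean | max | mean hides a value of at least 3? |
|---|---|---|---|---|
| 2.0 | 3.5 | 2.75 | 3.5 | yes |
| 2.5 | 3.4 | 2.95 | 3.4 | yes |
| 2.8 | 3.2 | 3.00 | 3.2 | no |
| 2.0 | 4.5 | 3.25 | 4.5 | no |

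The 3xULN cut-off is from Protocol 8.1.1 and Appendix 7. The table shell's own cut-offs are not shown.

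**The case against.** The best case for leaving the text alone is that little is lost and much is covered elsewhere.

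- **Scheduled sampling is dense.** MAD labs run every second day from Day 2 to Day 18. SAD labs are taken at three post-dose times and at follow-up, as far as the schedule can be read. This stands.
- **Repeats follow an abnormal value.** If the trigger was a scheduled sample, the participant is already counted and only the grade can change. This stands too, although grade is what these tables report.
- **Liver monitoring falls mostly outside the window.** Appendix 7 has the participant withdrawn from treatment. Weekly checks then come mainly after the last dose plus 5 days that closes the on-treatment phase in SAP 11.4.1. This stands for weekly checks, less so for twice-weekly ones.
- **The information survives.** Clinically relevant changes are recorded as adverse events, liver events have tables 3.20 and 3.47, all values are listed, and dose escalation rests on separate reviews. All true.
- **The averaging rule may not reach grading.** In SAP 3.2 it follows the sentence on baseline, and SAP 11.6.1 ties it to summary statistics. That is a fair reading, and it is why averaging is only a conditional, secondary point here.
- **Equal opportunity.** Scheduled-only tables give each participant the same number of chances to show a worst value. This is a real merit and the one genuine cost of the fix.
- **The shells may already use all values.** They are not in the documents, so this cannot be confirmed. As written, the SAP text governs.

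**Conclusion.** The point holds and is minor. A stated rule, followed literally, can understate a maximum grade that the same plan promises to report, and can put tables at odds with listings. The number of participants affected cannot be derived. Per participant the ceiling is 16.7 points in a six-active group and 4.2 points at 200 mg once daily. The any-abnormality rate does not move when a scheduled value was already abnormal. The conclusion assumes that the written rule, and not an unseen shell, drives the programming.

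A reader might infer more than the documents support:

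- **That the maximum-QTc tables share the fault.** They should not be pulled in. Protocol 8.1.2 allows QTc to be an average of triplicates, and Protocol 9.4.3.2 defines the reportable Holter value as a mean over replicates. Using single replicates would conflict with both.
- **That technically invalid samples stay in the tables.** Nothing says so, and SAP 3.2 requires data cleaning to be complete first.
- **That the plan is lopsided because of "the baseline value will be the latest pre-dose assessment with a non-missing value, including those from unscheduled visits" in SAP 5.2.** The table in that section names Day -2 of each period as the lab baseline displayed, which undercuts the contrast.
- **That the Part 1 on-treatment window is part of the defect.** Unscheduled values are excluded however SAP 11.4.1 is read, so that is a separate question.
- **That a table has already gone wrong.** The blinded summaries in Protocol 3.2.2 list raised transaminases once each at SAD 200 mg, SAD 700 mg and MAD 50 mg. They do not give treatment arm or grade per event, or say whether repeats were drawn.

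**What to change.** In SAP 3.2 and 11.5.2, limit the scheduled-only rule to by-visit summaries and mean plots. Add one sentence: the laboratory worst-case/maximum-grade tables (3.11, 3.15, 3.19; 3.38, 3.42, 3.46), the treatment-emergent toxicity tables (3.12, 3.16; 3.39, 3.43) and the hepatobiliary tables (3.21; 3.48) use all post-baseline lab results in each table's existing window, scheduled and unscheduled, and grade the worst individual result instead of a same-time mean. Say explicitly that ECG and QTc replicate averaging is unchanged.

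The cost is a few sentences and a programming filter, on data already collected. The downside is that participants tested more often have more chances to show a worst value. A table footnote can say so.
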